6.2.12.1 Motor States

Variables will be obtained from the diary data as follows:

- ON-Time without troublesome dyskinesia
- ON-Time with troublesome dyskinesia
- Total ON-Time (ON-Time with and without troublesome dyskinesia)
- OFF-Time
- Asleep
- Missing (or invalid) entry (missing + invalid)

'ON' time is also referred to as 'good ON time' and is considered equivalent to 'ON time without troublesome dyskinesia'.

6.2.12.2 Identification of a Valid Diary

A valid diary will not have ≥ 2 hours of invalid data entries (i.e., ≥ 4 invalid entries) over a given 24-hour period. An invalid diary entry is defined as one having either more than one entry recorded in each half-hour interval, an unreadable entry, or the absence of an entry in a half-hour interval. The average diary information from 3 valid diaries (if available) for each visit will be used to calculate diary-based efficacy endpoints. If there are only 2 valid diaries for a visit, then the

QMD Ref: Worldwide-TMP-ST-005-7.0 Effective: 12Aug2019	Governing QMD: Worldwide-SOP-ST-001	
Confidentiality Statement		
This document is the property of Worldwide Clinical Trials Inc. and may not be duplicated, copied, altered or removed from company without prior approval from Worldwide Quality Assurance or in compliance with Worldwide Standard Operating Procedures.		
REF: Worldwide-TMP-QA-001f-1.3	Page 18 of 49	

Worldwide Clinical Trials Controlled Quality Management Document		
WORLDWIDE CLINICAL TRIALS	Sponsor:	Integrative Research Laboratories Sweden AB
	Protocol Number:	IRL790C005
STATISTICAL ANALYSIS PLAN. PHASE 2-3-4		

average information from the 2 valid diaries will be used. If only one diary is valid, information from the single valid diary will be used. If no valid diaries are available for a patient visit, then the diary information is considered missing.

Therefore, a Valid diary = diary where Missing + Invalid < 4 intervals. Diaries where Missing +Invalid ≥ 4 intervals will be excluded from the analysis.

6.2.12.3 Total Daily Hours in Each Motor State

Total daily hours for each motor state will be calculated as follows,

Total daily hours = Number of 30-minute intervals with corresponding motor state /2

6.2.13 Modified Unified Dyskinesia Rating Scale (UDysRS)

The modified Unified Dyskinesia Rating Scale (UDysRS) consists of two primary sections, Historical and Objective. For this study, Part 1 (On-Dyskinesia) of the Historical section will be administered, and Part 2 (Off-Dystonia) will be omitted. The Objective section consists of Part 3 (Impairment) and Part 4 (Disability) including a total of 11 items, each rated 0-4, where 0 = normal, 1 =slight, 2 =mild, 3 =moderate, and 4 =severe. The subtotals of the Objective parts are summed to give an overall score.

For efficacy analyses, the scores from the following parts will be analysed:

- Parts 1, 3, and 4 (sum score)
- Parts 1b and 4 (sum score)

6.2.14 Movement Disorder Society - Unified Parkinson's Disease Rating Scale (MDS-**UPDRS**)

The Movement Disorder Society-Unified Parkinson's Disease Rating Scale (MDS-UPDRS) consists of four parts:

- Part 1, non-motor aspects of experiences of daily living [nM-EDL] (13 items)
- Part 2, motor aspects of experiences of daily living [M-EDL] (13 items)
- Part 3, motor examination (18 items)
- Part 4, motor complications (6 items)

Each item is rated 0-4, where 0 = normal, 1 = slight, 2 = mild, 3 = moderate, and 4 = severe.

QMD Ref: Worldwide-TMP-ST-005-7.0 Effective: 12Aug2019	Governing QMD: Worldwide-SOP-ST-001	
Confidentiality	Statement	
This document is the property of Worldwide Clinical Trials Inc. and may not be duplicated, copied, altered or removed from company without prior approval from Worldwide Quality Assurance or in compliance with Worldwide Standard Operating Procedures.		
REF: Worldwide-TMP-0A-001f-1 3	Page 19 of 49	

Worldwide Clinical Trials Controlled Quality Management Document		
WORLDWIDE CLINICAL TRIALS	Sponsor:	Integrative Research Laboratories Sweden AB
	Protocol Number:	IRL790C005
STATISTICAL ANALYSIS PLAN. PHASE 2-3-4		

For efficacy analyses, the scores from the following parts will be analysed:

- Part 1 nM-EDL (13 items) (total score)
- Part 2 M-EDL (13 items) (total score)
- Part 3 Motor Examination (18 items) (total score)
- Part 4 Motor Complications (6 items) (total score)
- Question 1.6 Features of Dopamine Dysregulation Syndrome (1 item) (score)
- Questions 2.13 Freezing + Question 3.11 Freezing of Gait (2 items) (sum score)
- Question 4.1 Time Spent with Dyskinesias (1 item) (score).
- Question 4.2 Functional Impact of Dyskinesias (1 item) (score)

6.2.15 Definition of a Responder

Patients who achieve any improvement (that is, at least 1 hour increase) in average daily ON-time without troublesome dyskinesia at Week 12 will be considered 'responders' and 'non-responders' (less than 1 hour increase) otherwise. Patients with missing data at Week 12, or who withdrew prior to Week 12 will be classified as non-responders.

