Integrating this data with *in vitro* affinity and functional assessments for the main molecular targets in the dopamine receptor family (dopamine D3 and D2 receptors) indicates that efficacy in patients with PD could be expected at C_{max} levels below 0.5 μ M in plasma. In such patients, the dosing of mesdopetam is also likely to be personalized. Flexible dosing has been explored in two of the clinical studies (phase 1b and phase 2a). In this study (phase 2b) a dose-response analysis will be performed to evaluate three dose levels of mesdopetam (i.e. 2.5 mg, 5 mg and 7.5 mg b.i.d.). The dose-response analysis will give knowledge of the relationship among dose, drug-concentration in blood and clinical response (effectiveness & safety).

The dose levels to be used in this study have been selected based on previous clinical studies (see Section 4.6) where data indicates that clinically relevant efficacy may be achieved at the dose levels selected. The most commonly reported adverse event in patients randomized to mesdopetam in the phase 2a study was increased parkinsonism (during titration phase), and the finding of a possible dose dependent increase in OFF-time strongly suggest that lower doses than 10 mg b.i.d. should be explored in this forthcoming study. The finding of a strong trend towards improved general motor function in patients allocated to 7.5 mg b.i.d. or lower indicate that the efficacy of mesdopetam may extend beyond that of reducing peak dose dyskinesia.

The treatment starts with a one-week dose run-in period where all patients are randomized to a starting dose of 5 mg mesdopetam or placebo (twice daily). Thereafter the patients are allocated to one of three doses of mesdopetam or placebo. Given the plasma half-life of about 7 hours, enough coverage during the waking hours of the day is expected.

4.4.Trial conduct

This study will be conducted in compliance with the protocol and according to International Conference on Harmonisation Good Clinical Practice Revision 2 (ICH GCP (R2)) and applicable regulatory standards. No deviation from the protocol will be implemented without the prior review and approval of the ethics committee and regulatory authorities except where it may be necessary to eliminate an immediate hazard to a research subject. In such case, the deviation will be reported to the ethics committee and regulatory authorities as soon as possible.

4.5.Population

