11.2.3. Assessments related to the primary endpoint

11.2.3.1. 24-hour patient home diary

Home diaries have gained wide acceptance as endpoints for clinical development of therapeutics aiming to reduce treatment-related motor complications [10]. Motor fluctuations and dyskinesia are associated with compromise in activities of daily living (ADL) and health-related quality of life. For this clinical trial patients will record their 24-hours motor function in 30-minute intervals, beginning at midnight. For each 30-minute interval the patient will rate the state he or she has been in for the past 30 minutes; OFF, ON (without troublesome dyskinesia) or ON with troublesome dyskinesia. The patient will also denote the time when he or she has been asleep.

It has been demonstrated that OFF-time and ON-time with troublesome dyskinesia are generally considered by patients to be "bad time" with regard to motor function, whereas ON-time without troublesome dyskinesia are generally considered to be "good ON-time" [11].

In general, an "OFF" time reduction or "good ON-time" increase of 1 hour may be considered clinically significant and has been used as an assumption in power calculations in clinical trials [10]. Therefore, it can be assumed that shift towards more "good ON-time" of a minimum of 1-hour daily represents a clinically meaningful effect, considering the total time spent in the daily ON state (ON with and without troublesome dyskinesia) is not negatively affected by the treatment.

For this trial, patient diary concordance training to improve accuracy and compliance is essential. Patients will be instructed and trained on how to complete the home diary at the screening visit or during a separate scheduled visit after receipt of the screening lab results and

Confidential	Version: 5.0	Page 51 of 74
Protocol: IRL790C005	Date: 5 Mar 2021	

prior start of the baseline diary completion period. The Investigator must ensure that each patient understands how and when to complete diaries before leaving the clinic.

The patient will receive instruction on how to complete the 24-hour home diary, including the definitions of ON and OFF. The definitions of ON and OFF will be reviewed, including ON time according to dyskinesia categories "without troublesome dyskinesia" and "with troublesome dyskinesia", with emphasis on the need for the patient to be consistent in their use of the definitions when rating their status in the 24-hour home diary during the study.

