6.14.3 Improvement in Daily ON-time, Responder Analysis

The number and percent of responders (at least 1h improvement in average daily ON-time) versus non-responders at Week 12 will be tabulated by treatment group.

Each dose level will be compared to placebo using a Cochran-Mantel-Haenszel (CMH) test. The risk difference for each dose level compared to placebo, corresponding 95% CI and p-value for the CMH statistic will be provided.

The following is the sample SAS code that will be used for this analysis:

```
PROC FREO DATA=DATAIN;
TABLES TRT01PN*RESP / RISKDIFF CMH;
ODS OUTPUT RISKDIFFCOL2 = RISK CMH = CMH PVAL;
RUN;
```

Where TRT01PN = Planned Treatment Group Number; RESP = Responder (0/1).

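### The responder rule uses the protocol's 1 h gain in good ON-time without the protocol's qualifier on total ON-time, and no planned output shows whether the patients counted as responders lost total ON-time

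*SAP*

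**What the plan says.** SAP 6.2.15 opens its definition of a responder with "Patients who achieve any improvement (that is, at least 1 hour increase) in average daily ON-time". The state meant is good ON-time, free of troublesome dyskinesia, and the time point is Week 12. Anyone gaining less than 1 h is a non-responder. The one further condition concerns missing data: "Patients with missing data at Week 12, or who withdrew prior to Week 12 will be classified as non-responders". Neither total ON-time nor OFF-time enters the rule. SAP 6.14.3 tabulates responders by arm and promises a CMH test and a risk difference for each dose against placebo.

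The 1 h figure has its rationale in protocol 11.2.3.1, on the home diary. There a daily shift of at least 1 h towards good ON-time is taken to matter clinically. The same sentence adds a qualifier: "considering the total time spent in the daily ON state (ON with and without troublesome dyskinesia) is not negatively affected by the treatment".

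The SAP also plans MMRM analyses of average daily OFF-time (3.3, 6.13.2.1) and total ON-time (3.4, 6.13.3.5), with charts of the motor states by arm and visit. The responder analysis is exploratory. SAP section 9 lists it among the changes from the protocol by title only, with no comment on the missing qualifier.

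**The concern.** A patient can gain good ON-time while troublesome ON-time turns mostly into OFF-time. The protocol has reason to watch for this. Its dose rationale (4.3) says that "the finding of a possible dose dependent increase in OFF-time strongly suggest that lower doses than 10 mg b.i.d. should be explored", and it names increased parkinsonism as the most commonly reported adverse event on mesdopetam in phase 2a. A responder percentage at 1 h will be read as the share of patients with a worthwhile benefit, because 1 h is the value the protocol justifies on that ground. The planned means cannot say whether the patients who gained good ON-time are the ones who lost total ON-time.

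Two smaller defects sit in the same analysis. The phrase *any improvement* does not mean a gain of at least 1 h: half-hour counts averaged over three diaries move in steps of 0.5/3 = 1/6 h. And the 6.14.3 sample code crosses all four arms with response in one table, with no stratum variable.

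**Working it through.** **The plan's own figure.** The documents give no responder rate or power for this analysis. The only power figure is for the primary endpoint: difference 3 h, SD 3.5 h, 31 evaluable per group. 3 / (3.5 × √(2/31)) = 3 / 0.889 = 3.37; 3.37 − 1.96 = 1.41; Φ(1.41) = 92%. The stated 92% reproduces (91.3% with the t distribution). It does not bear on the responder rule, but it supplies the SD of 3.5 h used below.

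**Does the rule admit the case?** Take a hypothetical patient, in hours per day:

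| | Good ON | Troublesome ON | OFF | Asleep | Total ON |
|---|---|---|---|---|---|
| Baseline | 6 | 5 | 5 | 8 | 11 |
| Week 12 | 7 | 1 | 8 | 8 | 8 |
| Change | +1 | −4 | +3 | 0 | −3 |

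Under SAP 6.2.15 this patient is a responder.

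**How often might it happen?** This is an illustration. The documents give no SD for change in OFF-time or total ON-time. Assumptions: change in troublesome ON-time dT has SD 2.8 h, change in OFF-time dO has SD 2.1 h, both are normal and uncorrelated, and sleep is constant.

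- Change in good ON-time G = −dT − dO, with SD √(2.8² + 2.1²) = 3.5 h.
- Change in total ON-time = −dO, and its correlation with G is 2.1/3.5 = 0.6.
- P(responder) = 1 − Φ((1 − mean G)/3.5).

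The fall in total ON-time among responders comes from the bivariate normal distribution:

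| Mean dT, mean dO | SAP responders | Also no fall in total ON | Also no fall beyond 1 h | Responders with any fall | Responders losing more than 1 h |
|---|---|---|---|---|---|
| 0, 0 (no effect) | 39% | 29% | 35% | 25% | 11% |
| −3 h, 0 | 72% | 44% | 57% | 38% | 20% |
| −3 h, +1 h | 61% | 28% | 40% | 55% | 34% |

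Against a placebo arm with no change, the difference in the last row is 61 − 39 = 22 points under the SAP rule, about −2 points if any fall disqualifies, and about 6 points with a 1 h tolerance. In the middle row it is 33, 15 and 23 points.

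**Sensitivity.** With a correlation of −0.3 between dT and dO (SD of G then 2.95 h), the any-fall shares of 38% and 55% become 43% and 59%. More generally, take SD 3.5 h for G, mean gains of 0, 1 or 3 h, no mean change in total ON-time, and a correlation of 0 to 0.6 between G and total ON-time. Then 25% to 50% of SAP responders have some fall. If mean total ON-time drops by 1 h (mean gain 1 or 3 h, total ON-time SD 1.5 to 2.5 h), the range is 47% to 75%.

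**Code.** SAP 6.14.3 says each dose is compared with placebo. A single four-by-two table tests the arms jointly, and a risk difference is defined for a two-by-two table. Randomisation was stratified at 6 h of troublesome ON-time (SAP section 5) and the primary model carries that factor, but the responder code does not.

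**The case against.** The protocol's qualifier ends with the words about the effect of the treatment, and the sentence speaks of what can be assumed. It reads naturally as a statement about a treatment effect in a group. On that reading the planned OFF-time and total ON-time analyses cover it, and a dose that converted troublesome ON-time into OFF-time would show there. The SAP also never calls a responder clinically meaningful. All of this stands, and leaves only the within-patient link uncovered.

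The evidence of risk is mixed. Protocol 4.3 speaks only of a possible OFF-time increase and goes on to report a strong trend to better general motor function at 7.5 mg b.i.d. or lower. Protocol 4.6 reports no evidence of changed OFF-time in phase 2a. A reader might infer that trading dyskinesia for OFF-time is an established effect at the study doses; the documents do not say so.

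A reader might also infer from the illustration that the responder benefit vanishes once total ON-time is considered. That needs the assumed 1 h OFF-time increase together with a zero-tolerance condition. With no mean OFF-time increase the benefit remains, at 44% against 29%.

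Nor do the documents support replacing the definition with a zero-tolerance rule. A patient who gains 4 h of good ON-time and loses 1/6 h of total ON-time would fail it. Troublesome ON-time that becomes sleep lowers total ON-time too. A valid diary may hold three missing or invalid half-hours (1.5 h), and SAP 6.2.12.3 counts hours without rescaling, so blanks alone can lower the total.

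The phrase *any improvement* is settled by its parenthesis, so that edit is only tidying.

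**Conclusion.** The point holds in a limited form. The SAP applies the 1 h threshold to individual patients without the qualifier that protocol 11.2.3.1 attaches to it, and no planned output links a patient's gain in good ON-time to his or her change in total ON-time. The text settles that much. How many responders would be affected is not known: the 25% to 75% range rests on assumed SDs, effects and correlations, and counts falls of any size, diary noise included.

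The consequence is confined to how one exploratory percentage is read. It sits outside the testing hierarchy of SAP 6.15, so the primary conclusion, alpha and power do not change. It is also not the only patient-level display: shift tables are planned for MDS-UPDRS question 4.2 and for CGI-S of dyskinesia. The mismatch between text and code in 6.14.3 is a plain error, independent of the illustration.

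**What to change.** - Keep the current responder row as defined.
- Before unblinding, add to SAP 6.2.15 and 6.14.3 a supplementary row for patients with at least 1 h gain in good ON-time and no reduction in average daily total ON-time beyond a tolerance that the sponsor states in advance. A cross-tabulation of responders by direction of total ON-time change would serve as well. Treat missing Week 12 data as in the main row. If unblinding has already taken place, label the addition post hoc.
- Delete *any improvement* and its parenthesis, and state the 1 h rule directly.
- Correct the 6.14.3 code so that each dose is set against placebo in its own table, with the CMH test and the risk difference stratified by the randomisation factor (<6 h, ≥6 h).

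The cost is a little extra SAP text and programming. Good ON-time and total ON-time are already derived in SAP 6.2.12.1, so no new data are needed. The added row will show a lower percentage than the current one.

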6.2.16 Definition of Adjusted Dose Group

To account for patients who have a permitted dose reduction and remain stable thereafter, adjusted dose groups will be defined. Patients randomly allocated to mesdopetam and who had a permitted dose reduction of 2.5 mg recorded at Visit 3, will be counted in the treatment group one dose lower than their randomized treatment. Patients randomly allocated to placebo but who had a dose reduction will remain in the placebo group.

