Fifteen (15) patients were randomized to treatment, 11 to mesdopetam and 4 to placebo. Generally, AEs were of mild intensity and transient after dose adjustments. Ten (10) patients in the mesdopetam treated group and 4 patients in the placebo group reported at least one related AE. Nervous system disorder was the most common AE (31% of all reported AEs). Five patients treated with mesdopetam reported transient worsening of parkinsonism during dose titration, an adverse effect which was mitigated by dose reduction. Thirteen (13) patients completed the study, 9 patients on mesdopetam and 4 patients on placebo. Two (2) patients treated with mesdopetam discontinued treatment due to AEs.

IRL790C003 (Phase 2a)

In the Phase 2a study (IRL790C003), 75 patients with advanced PD experiencing LID were randomized to receive mesdopetam or placebo as adjunct treatment for 28 days, 39 to mesdopetam and 36 to placebo. During the first two weeks of treatment dosing was gradually increased until signs of intolerability occurred, after which dose adjustments were made. Following this titration, the dosing was kept stable for the remaining two weeks.

Generally, AEs were of mild intensity and transient after dose adjustments. Parkinsonism was the most common AE. Nine patients in the mesdopetam treated group reported parkinsonism during titration only and 2 patients in the mesdopetam treated group reported parkinsonism during steady state. 72 patients completed the study, with 37 patients on mesdopetam and 35 patients on placebo. 3 patients discontinued treatment in advance due to AEs (two on mesdopetam and one on placebo).

Vital signs, laboratory measurements and cardiovascular functions were unaffected by mesdopetam treatment.

At EOT the number of daily hours spent in ON-phase with troublesome dyskinesia was significantly reduced for mesdopetam treated patients as compared to placebo. General mobility was unaltered by the treatment, there were no evidence for changes in time spent in OFF-state or in the total score of MDS-UPDRS parts 2 or 3.

The clinical studies show that, following individualized dose adjustment, mesdopetam is well tolerated in patients with advanced PD and seem to act to reduce dyskinesia without compromising general motility.

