	A dose reduction is only allowed if the patient experiences an increase in parkinsonism and/or a consistent increase in motor OFF-time. Increased parkinsonism is manifested as consistent increase in disability associated with parkinsonian symptoms (i.e. bradykinesia, tremor and/or rigidity).
	The following steps are permitted if the dose is decided to be reduced:
	Patients allocated to 7.5 mg b.i.d. \rightarrow dose is reduced to 5 mg b.i.d.
	Patients allocated to 5 mg b.i.d. \rightarrow dose is reduced to 2.5 mg b.i.d.
	Patients allocated to 2.5 mg b.i.d. \rightarrow dose is maintained (i.e. 2.5 mg b.i.d.).
	Patients allocated to placebo b.i.d. \rightarrow placebo b.i.d. is maintained.

Confidential	Version: 5.0	Page 40 of 74
Protocol: IRL790C005	Date: 5 Mar 2021	C

	If parkinsonism is still increased following this dose reduction, the patient and Investigator need to decide if the patient could continue with the same dose in the study (since the dose cannot be reduced further) or if the patient have to withdraw the IMP and the study. Dose reduction will be managed through the IRS system.
Patient motor function review performed at Visit 3 (Day 28 ±4 days)	This review is based on the 24-hour patient home diaries completed in the week prior to Visit 3 and the MDS-UPDRS part II assessment completed during site Visit 3. Diaries and MDS-UPDRS data are reviewed and compared to baseline.
	If there is a clinically relevant increase in OFF-time, the Investigator must determine if the increase has been consistent over time and if it is predominantly related to non-motor or motor OFF-time (according to the Investigator's clinical judgement). Evaluation of results from MDS-UPDRS part 2 (M-EDL) should be weighted in the decision. Adherence to prescribed antiparkinsonian medications should also be reviewed.
	Should a consistent increase in motor OFF-time, and/or a clinically significant worsening of mobility due to parkinsonism be assessed as likely due to the IMP, the dosing should be reduced by 2.5 mg b.i.d. at this visit. If the patient has already had a dose reduction prior to Visit 3, the dose cannot be reduced further at this visit, and the Investigator must determine whether the patient can continue in the study (i.e. continue in the study with the same dose).
	Other AEs not relating to the core symptoms of parkinsonism (such as, fatigue, headache, dystonia and other) do not qualify for dose reduction.

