6.17 Safety Analyses

Safety analyses will be presented by actual treatment group as well as adjusted dose group for all patients in the SAS.

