6.17.1 Adverse Events

Adverse events will be collected from the time of informed consent and continues through the last follow-up assessment in the study.

A treatment emergent adverse event (TEAE) is defined as:

- Any AE that has an onset on or after the first dose of study drug through the last follow-up assessment in the study.
- Any pre-existing AE that has worsened in severity on or after the first dose of study drug through the last follow-up assessment in the study.

A treatment-related AE is defined as an AE relationship to study drug classified by the Investigator as 'possible', or 'probable'. If an AE has missing relationship, 'probable' will be assumed for analysis purposes.

Severity of the AE will be graded using the Common Terminology Criteria for Adverse Events (CTCAE) grading system (Version 5.0): Grade 1 (Mild), Grade 2 (Moderate), Grade 3 (Severe), Grade 4 (Life-Threatening), Grade 5 (Fatal). Grade 3 (Severe) will be assumed for an AE with missing grade.

An overall summary table of AE incidence (number and percent of patients) and number of events, will be presented by treatment group and overall, for the following categories:

Any Reported TEAE

 QMD Ref: Worldwide-TMP-ST-005-7.0 Effective: 12Aug2019
 Governing QMD: Worldwide-SOP-ST-001

 Confidentiality Statement

 This document is the property of Worldwide Clinical Trials Inc. and may not be duplicated, copied, altered or removed from company without
 prior approval from Worldwide Quality Assurance or in compliance with Worldwide Standard Operating Procedures.

 REF: Worldwide-TMP-QA-001f-1.3
 Page 42 of 49

- **Treatment-Related TEAEs**
- Serious TEAEs
- Serious Treatment-Related TEAEs
- TEAEs Leading to Reduction in Dose of Study Drug
- TEAEs Leading to Interruption of Study Drug
- TEAEs Leading to Withdrawal of Study Drug
- TEAEs Leading to Early Withdrawal from Study •
- **TEAEs** Leading to Death •

Summaries of TEAE incidence and number of events by SOC and PT will be presented by treatment group and overall, for the following:

- TEAEs
- Treatment-related TEAEs •
- Serious TEAEs
- Serious Treatment-Related TEAEs
- TEAEs by Maximum Grade, (incidence only)
- Treatment-Related TEAEs by Maximum Grade, (incidence only)
- TEAEs by Strongest Relationship, (incidence only)
- Treatment-Related TEAEs by Strongest Relationship, (incidence only)

The following listings of AEs will be presented in Section 14.3.2 of the CSR:

- Serious AEs
- TEAEs Leading to Interruption of Study Drug

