- TEAEs Leading to Withdrawal of Study Drug
- TEAEs Leading to Early Termination from Study
- Deaths

TEAE tabulations will be presented by SOC and PT in descending frequency of AE incidence in the pooled mesdopetam arm and then alphabetically for ties.

All reported AEs will be listed in Appendix 16.2.7 of the CSR with separate listings for TEAE and non-treatment-emergent AEs (NTEAE).

Overall ongoing TEAEs will be summarized by month 1, 2, and 3. Additionally, TEAEs that occur in >5% of all participants will be summarized by month 1, 2, and 3.

QMD Ref: Worldwide-TMP-ST-005-7.0 Effective: 12Aug2019	Governing QMD: Worldwide-SOP-ST-001		
Confidentiality Statement			
This document is the property of Worldwide Clinical Trials Inc. and may not be duplicated, copied, altered or removed from company without prior approval from Worldwide Quality Assurance or in compliance with Worldwide Standard Operating Procedures.			
REF [·] Worldwide-TMP-OA-001f-1 3	Page $43 \text{ of } 49$		

Worldwide Clinical Trials Controlled Quality Management Document		
WORLDWIDE CLINICAL TRIALS	Sponsor:	Integrative Research Laboratories Sweden AB
	Protocol Number:	IRL790C005
STATISTICAL ANALYSIS PLAN. PHASE 2-3-4		

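### The adjusted-dose safety tables place adverse events that began before a dose reduction, including those that caused it, under the lower dose

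*SAP*

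**What the plan says.** SAP 6.2.16 defines an adjusted dose group. A patient randomized to mesdopetam with a permitted 2.5 mg reduction recorded at Visit 3 "will be counted in the treatment group one dose lower than their randomized treatment". Placebo patients with a reduction stay in placebo.

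SAP 6.17 carries this into safety: "Safety analyses will be presented by actual treatment group as well as adjusted dose group for all patients in the SAS".

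SAP 6.17.1 defines a TEAE by onset or worsening at any time from first dose to last follow-up. SAP 6.3.4 counts events per patient over the patients in the group. One summary row is "TEAEs Leading to Reduction in Dose of Study Drug".

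Protocol 9.2 Table 3 limits the reason for reducing: "A dose reduction is only allowed if the patient experiences an increase in parkinsonism and/or a consistent increase in motor OFF-time". The decision can be made only from Visit 2 (Day 9) to Visit 3 (Day 28 ± 4 days). Patients on 2.5 mg or placebo keep their dose, and reductions run through the IRS so that the blind holds.

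**The concern.** The grouping moves the whole patient, with every TEAE since first dose, to the dose taken last. A reduction has one permitted kind of cause, and that cause must precede it. Where the cause was recorded as a TEAE, it began on the higher dose, yet the adjusted table shows it under the lower one.

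Protocol 6.2 expects the study to describe how dose relates to effectiveness and safety. Parkinsonism was the most common AE in Phase 2a, and Protocol 4.6 says of it: "Nine patients in the mesdopetam treated group reported parkinsonism during titration only". Two more mesdopetam patients had it at steady state. The event most exposed to misplacement is thus a leading tolerability signal, and one that tended to come early, although that study titrated upward and this one does not.

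**Working it through.** No figure stated in the plan bears on this point. The check is a reading of the rules together, followed by an illustration on assumed counts.

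**1. Where each event goes.** Take a patient randomized to 7.5 mg and reduced on Day 28 of 84.

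| Period | Dose taken | Adjusted-table column | Correct dose? |
|---|---|---|---|
| Run-in, Days 1–8 | 5 mg | 5 mg | yes |
| Visit 2 to reduction, Days 9–27 | 7.5 mg | 5 mg | no |
| After reduction, Days 28–84 | 5 mg | 5 mg | yes |

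For a patient reduced from 5 mg, events from Visit 2 to the reduction stand under 2.5 mg.

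**2. Does another rule correct this?** "Overall ongoing TEAEs will be summarized by month 1, 2, and 3" splits by calendar time and states no dose at onset. SAP 6.10 splits exposure at the dispensing date of the changed dose, but the AE tables do not use that split. As written, its periods also overlap: (9−1+1) + (28−9+1) + (84−28+1) = 9 + 20 + 57 = 86 days. Without double-counting the switch days they are 8 + 19 + 57 = 84.

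**3. Effect on incidence.** Inputs:
- n = 38 per arm, from the 154 randomized in SAP section 4 (154/4 = 38.5).
- e75 and e5: patients with a parkinsonism-type TEAE on 7.5 mg and 5 mg. Assumed.
- k and m: captured reducers on 7.5 mg and 5 mg. Assumed.
- tk and tm: those reducers with such a TEAE. Assumed.

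Adjusted 7.5 mg = (e75 − tk)/(n − k).
Adjusted 5 mg = (e5 − tm + tk)/(n − m + k).

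The 7.5 mg rate falls if and only if tk/k > e75/n.

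Base A is 11/38 = 28.9% v 5/38 = 13.2%, gap 15.8 points. The first figure is close to the Phase 2a (9 + 2)/39 = 28.2%; the second is assumed. Base B is 6/38 = 15.8% v 3/38 = 7.9%, gap 7.9, both assumed.

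| Base | k, m | Reducers with a TEAE | Adjusted 7.5 mg | Adjusted 5 mg | Gap (points) |
|---|---|---|---|---|---|
| A | 2, 1 | all | 9/36 = 25.0% | 6/39 = 15.4% | 9.6 |
| A | 2, 1 | none | 11/36 = 30.6% | 5/39 = 12.8% | 17.7 |
| A | 4, 2 | all | 7/34 = 20.6% | 7/40 = 17.5% | 3.1 |
| A | 4, 2 | half | 9/34 = 26.5% | 6/40 = 15.0% | 11.5 |
| A | 4, 2 | none | 11/34 = 32.4% | 5/40 = 12.5% | 19.9 |
| A | 6, 3 | all | 5/32 = 15.6% | 8/41 = 19.5% | −3.9 |
| B | 2, 1 | all | 4/36 = 11.1% | 4/39 = 10.3% | 0.9 |
| B | 2, 1 | none | 6/36 = 16.7% | 3/39 = 7.7% | 9.0 |

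The rows with none are possible because a reduction can follow from the Visit 3 diary and MDS-UPDRS part 2 review, after which "the dosing should be reduced by 2.5 mg b.i.d. at this visit", without an AE having been recorded.

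**4. The reduction row.** Each captured reduction for a TEAE moves one column down, whatever the reduction rate. Suppose 4 and 2 reductions for TEAEs on 7.5 mg and 5 mg, all captured, and assume no blinded reductions on 2.5 mg. By arm the row for 7.5, 5 and 2.5 mg is 4/38, 2/38, 0/38. Adjusted, it is 0/34, 4/40, 2/40. If one of the four 7.5 mg reductions was not recorded at Visit 3, the adjusted row is 1/35, 3/39, 2/40.

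**The case against.** The strongest reply is that two displays are planned and their errors are complementary. In the example above, the 7.5 mg reducer spends 8 + 57 = 65 of 84 days (77%) on 5 mg. The assigned-arm table puts all of that time under 7.5 mg, while the adjusted table places it correctly. All AEs are also listed, and Protocol 14.10 plans no formal safety tests. This stands, and it limits the consequence. It does not justify attributing the cause of a reduction to the dose that followed it.

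A reader might infer more than the documents support:

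- *That all earlier events are misplaced.* Run-in events of 7.5 mg reducers did occur on 5 mg.
- *That the adjusted 7.5 mg reduction row must be empty.* The rule captures only permitted reductions recorded at Visit 3. A patient who reduced and left before then stays in the randomized group.
- *That the 2.5 mg row must be zero in the assigned-arm table.* Investigators are blinded, and Protocol 12.6 lists dose reduction as a recordable action. SAP 6.2.16 itself foresees reductions on placebo. Reductions that changed no dose can therefore be recorded on 2.5 mg and placebo, so the zero in the example is an assumption.
- *That the gradient must flatten or reverse.* Reducers without a recorded TEAE widen the gap. The reversal appears only in the most extreme case shown.
- *That these tables will decide the Phase III dose.* No passage says so. The Phase III remark in Protocol 14.1 concerns confidence intervals for effect size.

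**Conclusion.** The fault is real and confined to the adjusted-dose safety tables. TEAEs that began on the randomized dose between Visit 2 and a captured reduction are tabulated under a dose to which the patient had not yet been reduced. That attribution follows from the rules alone and needs no assumed rate.

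Its effect on incidence by dose cannot be sized, because the documents give neither the reduction rate nor the share of reducers with a recorded TEAE. Under the assumed counts the gap between 7.5 mg and 5 mg can shrink, widen or, in one extreme case, reverse. The parallel tables remain usable, provided the actual treatment group means the assigned arm; the SAP does not say so for a patient who took two doses. The point is worth correcting because the rule is wrong for the events that matter most to it, and because the correction is cheap. It has no bearing on the primary efficacy analysis.

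**What to change.** In SAP 6.17:

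1. Report TEAEs leading to a dose reduction by the dose taken at onset. Keep blinded reductions that changed no dose under the assigned group.
2. Either limit the adjusted-dose TEAE tables to onset after Visit 3, with patients dosed after Visit 3 as the denominator, or replace them with a descriptive table by dose at onset. The first option matches the window that Protocol 14.9.2 sets for its treatment-received analysis of the primary endpoint. The second can use the SAP 6.10 dispensing dates, made non-overlapping, with patient-days and a switch-day convention.
3. Label these tables as not a randomized comparison. Keep the assigned-arm tables as the main safety presentation, and state that the actual treatment group means the assigned arm unless the wrong dose was dispensed.

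SAP 6.2.16 and Protocol Table 3 must also be reconciled for patients randomized to 2.5 mg: the SAP exempts only placebo from the move down, while Table 3 keeps 2.5 mg unchanged.

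The cost is modest programming from dates already collected. With the post-Visit 3 option, early events appear only in the assigned-arm tables. With the dose-at-onset option, dose is confounded with time and intolerance, and a patient can appear under more than one dose. The switch-day convention is needed because Protocol 12.8 requires AE start times only for the first dosing day.
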